## 7.7 Reportable events

Reportable events will be coded using MedDRA and evaluated for FAS. Incidence rates will be calculated with respect to System Organ Class and Preferred Term.

Details of reportable events will be listed including the following information:

- PatientID
- Onset date
- End date
- Ongoing at the end of study
- Event diagnosis (MedDRA coding)
- Action taken
- Severity
- Relationship to LCIG
- Serious adverse event (no/yes)

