#### 4.2.1 Inclusion criteria

Patients were eligible for study participation if all of the following criteria were fulfilled:

- 1. Patients diagnosed with APD and on LCIG treatment for at least 12 months
- 2. Patient must have been on continuous LCIG treatment for at least 80% of days in the preceding year
- 3. Patients must be treated by the same physician (PI or co-investigator) since the initiation of LCIG treatment
- 4. Decision to treat with LCIG was made and therapy was started by the physician prior to any decision to approach the patient to participate in this study
- 5. Prior to any data collection, the patient, or legal authorized representative (LAR) has voluntarily signed an Authorization for Use/Disclosure of Data (AUDD)/informed consent form (ICF) according to national regulations after the study has been explained and the subject has had the opportunity to have questions answered

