## 5 Analysis data set

One analysis set will be used:

The full analysis set (FAS) consists of all patients enrolled who fulfill the patient selection criteria.

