#### 7.4 Patient data

Patient disposition will be evaluated for all patients enrolled.

All other variables will be evaluated for FAS according to the methods described in Section 7.1.

Patient data will be analyzed overall and separately for the following three groups:

- Patients on monotherapy 1 at 12 months after LCIG infusion (see Section 6.4)
- Patients on monotherapy 2 at 12 months after LCIG infusion (see Section 6.4)

Patients not on monotherapy 2 at 12 months after LCIG infusion (see Section 6.4) For duration of 'Off' state (hours) and duration of dyskinesia (hours) the difference will be calculated between the time points 'prior to LCIG initiation' and visit (UPDRS IV: modified items 39 and 32) as value at visit minus value prior to LCIG initiation.

'Other' co-morbidities will be coded using MedDRA. Incidence rates will be calculated with respect to System Organ Class and Preferred Term.

Regarding the 'Historical therapy discontinued prior to considering LCIG initiation' patient based means that a therapy type will only be counted once per patient.

A list of other medications and therapies only for indications secondary to PD will be provided including the following information:

- PatientID
- Name of concomitant medication or therapy
- Indication
- Total daily dose
- Dose unit
- Start date
- End date
- Ongoing at the end of study

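### Reportable events are evaluated only in the full analysis set, so events collected from enrolled patients who violate a selection criterion have no place in the planned safety tables

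*SAP*

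**What the plan says.** SAP 5 opens with "One analysis set will be used" and defines it: "The full analysis set (FAS) consists of all patients enrolled who fulfill the patient selection criteria". SAP 7.7 then says "Reportable events will be coded using MedDRA and evaluated for FAS", and continues "Incidence rates will be calculated with respect to System Organ Class and Preferred Term". The listing follows in the same section, introduced by "Details of reportable events will be listed including the following information", with no population of its own.

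The only analysis on a wider population is in SAP 7.4: "Patient disposition will be evaluated for all patients enrolled". The next sentence there sends the rest of the patient data back to the FAS: "All other variables will be evaluated for FAS according to the methods described in Section 7.1". SAP 6.3 foresees enrolled patients who break a criterion and plans a list of them under patient disposition, but attaches no event data to that list.

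Collection is wider than analysis. Protocol 9.3.1 asks for all adverse events, product complaints and pregnancies. Protocol 11.1.4 starts SAE reporting at authorization. Protocol 11.1.5.1 and SAP 4.4.6 add suspected adverse reactions from the retrospective period. None of these sections makes eligibility a condition. SAP 6.6 tabulates adverse reactions by LCIG phase (initiation and maintenance) and, separately, AEs, SAEs and adverse drug reactions after authorization.

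**The concern.** Failing a selection criterion can be a good reason to leave a patient out of the monotherapy percentages. It is not a reason to leave that patient's events out of an event count. A change of treating physician, or earlier participation in an interventional trial while on LCIG, does not make an adverse reaction on LCIG less valid.

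SAP 2.5 makes the described methods binding for programming. A programmer who follows the plan will therefore drop these patients from the MedDRA tables even though their events are in the database. At stake is the completeness of the study's own safety summary: adverse reactions before authorization, and AEs, SAEs, product complaints and pregnancies after it.

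Exclusion might also be related to the events. One criterion reads "Patient must have been on continuous LCIG treatment for at least 80% of days in the preceding year". A patient enrolled in breach of it had long interruptions, and protocol section 7.0 names device and procedure complications that may require further surgery.

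**Working it through.** **1. The plan's own figure.** Protocol 9.5 requires 385 evaluable patients for a two-sided 95% interval of ±5 points at 50%. Check: n = 1.96² × 0.5 × 0.5 / 0.05² = 384.15, rounded up to 385. This reproduces. Planned enrolment is about 400, so the room for non-evaluable patients is 400 − 385 = 15, and 15/400 = 3.75%. The protocol says only that few such patients are expected. It does not state 15, and it does not equate non-evaluable patients with selection-criteria violators. Using 15 as the number of violators is an assumption.

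**2. Collection against analysis.**

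| Item | Collected from | Analysed in |
|---|---|---|
| Disposition | all enrolled | all enrolled (SAP 7.4) |
| Adverse reactions before authorization | all enrolled (protocol 11.1.5.1, SAP 4.4.6) | FAS (SAP 7.7) |
| AEs and SAEs after authorization | all enrolled (protocol 9.3.1 and 11.1.4, SAP 4.4.6) | FAS (SAP 7.7) |
| Product complaints, pregnancies | all enrolled (protocol 9.3.1, SAP 4.4.6) | no set other than the FAS exists |

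The omission follows from the text alone and needs no assumption about rates.

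**3. Possible size.** Let k be the number of violators among 400, pF the proportion of FAS patients with an event, and pV the proportion of violators with one.

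- Patients with an event who are omitted: k × pV
- All-enrolled proportion: [(400 − k) × pF + k × pV] / 400
- Share of patients with events omitted: k × pV / [(400 − k) × pF + k × pV]

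The documents give none of these three inputs. With pF = 10% assumed throughout and pV from 10% to 40%:

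| k | Omitted patients with an event | All-enrolled proportion (FAS: 10.0%) | Share omitted |
|---|---|---|---|
| 4 | 0.4 to 1.6 | 10.0% to 10.3% | 1.0% to 3.9% |
| 15 | 1.5 to 6 | 10.0% to 11.1% | 3.75% to 13.5% |
| 40 | 4 to 16 | 10.0% to 13.0% | 10.0% to 30.8% |

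Worked case, k = 15 and pV = 40%: 385 × 0.10 = 38.5 and 15 × 0.40 = 6, so 44.5/400 = 11.1% and 6/44.5 = 13.5%.

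At equal rates the incidence does not move at all. Only the count is short, by k/400, which is 3.75% for k = 15.

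If violators have fewer events the shift reverses. With k = 15 and pV = 5%, 15 × 0.05 = 0.75 and (38.5 + 0.75)/400 = 9.8%, below the 10.0% in the FAS.

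**4. Which events the 80% criterion can touch.** It looks back over the year before inclusion; failing it means being off LCIG for more than 0.20 × 365 = 73 days. Complications that caused such interruptions lie mainly before authorization. They enter the data only as retrospective adverse reactions. The AE and SAE tables in SAP 6.6 cover events after authorization, so this criterion gives no direct argument about them.

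**The case against.** The strongest reply is that little is lost:

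- Safety is neither an objective nor an endpoint.
- Protocol 9.9 already limits safety conclusions, because patients who stopped LCIG are not captured.
- SAEs reach the sponsor within 24 hours whatever the analysis set (protocol 11.1.5).
- Protocol 12.1.2 promises that product complaints associated with adverse events will appear in the study summary.
- The listing in SAP 7.7 names no population, so it might be run on all enrolled patients.
- SAP 7.10 allows changes to the analyses.

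Most of this stands as a limit on importance, but none of it closes the gap. The limitation in protocol 9.9 concerns data that were never collected; here the data exist and would be set aside. Expedited reporting is separate from the study's event tables. The listing sits directly under the FAS sentence and is at best ambiguous. An option to modify is not a prespecified population.

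A reader might go further and infer that the reported SAE incidence is biased downward, because patients removed for interrupted treatment have more events. The documents do not support that. As shown above, the 80% criterion bears mainly on retrospective adverse reactions. An excess of those in patients who fail it is plausible, but nowhere stated. Other violations have no evident safety link (physician continuity, language or motivation), and some could act the other way: a patient with under 12 months on LCIG has a shorter retrospective window in which reactions could be recorded. The mix of violations is unknown.

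**Conclusion.** The point holds as a gap in the safety population. Under SAP 5 and 7.7, events collected from enrolled patients who violate a selection criterion are left out of the incidence tables and, on the natural reading, the listing. Expedited reporting is unaffected.

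The expected effect is modest. If up to 15 of about 400 patients are excluded, 3.75% of patients with events go uncounted at equal rates, with no change in the incidence itself. The share is larger if violators have more events. Both the 15 and every event rate used here are assumptions, and the direction of any bias is uncertain. Confidence is high in the reading of the text and low in any particular size. The correction is still worth making because it costs almost nothing and leaves the primary analysis and the sample size untouched.

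**What to change.** - **SAP 5:** add a safety set of all enrolled patients with valid signed authorization who received LCIG, whatever their status on the other selection criteria. Patients without valid authorization stay out.
- **SAP 7.7:** evaluate and list reportable events and product complaints in the safety set, state that population explicitly for both tables and listing, and flag selection-criteria violators in the listing. The FAS results may be shown alongside.
- **All other analyses:** keep the FAS.

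A smaller alternative, if the sponsor prefers to keep the FAS tables, is a separate listing of the events of excluded patients. That would make the events visible but leave them out of the incidence figures.

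The cost is a few sentences in the SAP and one more population flag. No new data are needed.

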As progressive deterioration of the nigrostriatal dopaminergic transmission occurs, even complex oral drug regimens may become insufficient for symptom control [2]. Therefore, other therapeutic strategies have been developed, including treatments based on continuous drug delivery (CDD) [3-5], such as continuous subcutaneous apomorphine infusion therapy (CSAI), or levodopa-carbidopa intestinal gel (LCIG), or even surgical interventions such as implantation of deep brain stimulation (DBS) devices. However, in treatment options such as CSAI and DBS, continued use of PD medication appears to remain necessary for many APD patients. In many cases, CSAI does allow for withdrawal or tapering of other PD treatments such as COMT-inhibitors, dopamine agonists, and MAO-B inhibitors, as well as reductions of levodopa dosages. Still, CSAI is only rarely used as monotherapy as this is often limited by poor tolerability of high doses of apomorphine [28-32]. Studies on DBS treatment show that, even though DBS may enable reductions in the dosing of PD medication by 35-60%, patients can very rarely be managed without any additional therapy [28, 33, 34].

Levodopa-Carbidopa Intestinal Gel (LCIG)

Various levodopa CDD formulations (intravenous and enteral) have been under investigation for already more than 30 years [35-37]. Among the enteric CDD formulations, levodopa-carbidopa intestinal gel (LCIG) is the only formulation of LD and carbidopa which has been found to be suitable for continuous long-term intestinal infusion so far [38]. The LCIG system has been on the market for over 10 years, and is currently approved in more than 40 countries in the treatment of levodopa-responsive APD. In the

majority of countries, it is marketed by AbbVie (AbbVie Ltd, United Kingdom) under the trade names Duodopa[®] and Duopa[®] (in the United States).

The LCIG suspension is provided in 100 mL cassettes to be connected to an ambulatory pump (CADD-Legacy[®] 1400 portable pump) that delivers the cassette content directly into the duodenum. The LCIG infusion rate is programmable and can be adjusted in steps of 0.1 mL/h (equivalent to 2 mg levodopa/h). In addition, patients can self-administer extra doses during the day by pressing a dose button to infuse a pre-programmed bolus (usually 10 to 20 mg per bolus). Patients may also (if instructed to do so by their treating physician) adjust the amount of the extra dose according to their needs.

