#### Clinical PD status immediately prior to / at LCIG initiation

- Duration of 'Off' state time during a 24h period (hours)
- Duration of dyskinesia during a 24h period (hours)
- Severity of dyskinesia
- Reason for LCIG start (multiple answers)
- Conduction of Nasojejunal test phase (yes, no)
  - If yes: reason (multiple answers)
  - If no: reason (multiple answers)
- Duration of titration calculated as date of titration finalization minus date of titration initiation +1
- Duration of LCIG treatment calculated as visit date minus date of LCIG initiation start +1
- Hospitalization for titration and PEG-J placement (yes, no)
- Hospitalization for PEG-J placement (yes, no)

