## 6.6 Reportable events and product complaints

- Separately for 'LCIG initiation' and 'LCIG Maintenance Treatment':
  - Any adverse reaction (yes, no; patient based)
  - Event diagnosis (MedDRA coding; patient based)
  - Action taken (event based)
- Events occurring after the time of patient authorization:
  - Reportable event (patient based):
    - Any adverse event (AE)
    - Serious adverse events (SAE)
    - Adverse drug reaction (ADR)
  - Event diagnosis (MedDRA coding; patient based): separately for AE, SAE, ADR
  - Any pregnancy which has not been reported to an AbbVie care Duodopa nurse (yes, no)
  - Any product complaint that has not been reported before (yes, no)
    - If yes: Complaint description (MedDRA coding; patient based)

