## 7 Statistical methodology

## 7.1 General methodology

All statistical analyses will be carried out by means of the SAS® package (version 9.4).

Quantitative data (e.g. age) will be described by the statistical parameters valid N, missing N, mean, standard deviation (SD), minimum, the 25%-quartile, median, the 75%-quartile, and the maximum.

Qualitative data (e.g. gender) will be presented by means of (absolute and relative) frequency distributions. If applicable, two methods will be followed for calculation of percentages. The first method considers missing data as a separate group, which results in the same sample size for all parameters. The second method of calculation is based on the valid data per parameter, excluding patients with missing values ("valid data analysis"). Accordingly, this results in different sample sizes. In general, description of results within the report refers to the "valid data analysis".

For categorical variables associated with score values, the mean will be calculated as well.

Two-sided 95% confidence intervals will be provided for the primary, and if applicable, the secondary variables defined by proportions.

Statistical methods which differ from the above mentioned methods or require further description will be addressed in the following sections.

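### The patient-based adverse reaction percentages for LCIG initiation and LCIG maintenance carry no time at risk and no phase boundaries, so they cannot be compared as risks

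*SAP*

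**What the plan says.** SAP 6.6 sets out the adverse reaction variables "Separately for 'LCIG initiation' and 'LCIG Maintenance Treatment". The first is "Any adverse reaction (yes, no; patient based") and the second is "Event diagnosis (MedDRA coding; patient based"). SAP 7.7 then states: "Incidence rates will be calculated with respect to System Organ Class and Preferred Term". It names the full analysis set but gives no denominator in time. No section of the protocol or SAP says when initiation ends and maintenance begins.

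Two other SAP sections show what the statistic must be. Section 7.1 says "Qualitative data (e.g. gender) will be presented by means of (absolute and relative) frequency distributions". Section 7.4 uses the same sentence for ticked co-morbidities: "Other' co-morbidities will be coded using MedDRA. Incidence rates will be calculated with respect to System Organ Class and Preferred Term". There, only a percentage of patients is possible.

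On observation time, SAP 4.2.1 requires at least 12 months on LCIG and sets no maximum. Protocol 7.0 notes that "The LCIG system has been on the market for over 10 years". SAP 4.4.6 collects every adverse reaction with onset before authorization, with no look-back limit. SAP 6.3 already derives "Duration of LCIG treatment calculated as visit date minus date of LCIG initiation start +1", and also a titration duration. The event listing in 7.7 holds the onset date. None of these enters the adverse reaction summary.

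**The concern.** The percentage of patients with at least one reaction accumulates with observation time. It can be read as a risk only when patients are observed for the same period, or when that period is reported with it. Neither is so here. Maintenance time varies between patients without an upper bound, and the two phases are not delimited, so their lengths are unknown and need not be similar.

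A table that splits reactions by phase under the label of incidence rates invites the reader to set one column against the other, and to set the maintenance column against the 12-week and 54-week trials cited in Protocol 7.0. The table would not support either reading, and nothing in it would warn the reader.

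**Working it through.** **The plan's own figures.** Neither document states an expected adverse reaction rate or a phase length, so there is no figure to reproduce on this point. The one calculation given, the study size, does reproduce: 1.96² × 0.5 × 0.5 / 0.05² = 384.2, rounded up to 385. It does not bear on this question. All rates and phase lengths below are therefore assumptions.

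**Step 1: effect of time alone.** With a constant rate r per patient-year over t years, the expected percentage with at least one event is 1 − exp(−r t). Four weeks is 28/365.25 = 0.0767 years.

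| Rate per patient-year | 4 weeks | 1 year | 5 years | 10 years |
|---|---|---|---|---|
| 0.05 | 0.4% | 4.9% | 22.1% | 39.3% |
| 0.10 | 0.8% | 9.5% | 39.3% | 63.2% |
| 0.50 | 3.8% | 39.3% | 91.8% | 99.3% |

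At 0.10 per patient-year in both phases, 4 weeks against 5 years gives 0.76% against 39.35%. That is about a 52-fold difference with no difference in rate.

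**Step 2: can the ranking of the phases mislead?** Assume 1.0 per patient-year in a 4-week initiation and 0.10 in maintenance.

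- Initiation: 1 − exp(−1.0 × 0.0767) = 7.4%.
- Maintenance: 9.5% at 1 year and 1 − exp(−0.10 × 4) = 33.0% at 4 years.

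The phase with one tenth of the rate shows the higher percentage. This depends on the pair of rates. With 5.0 per patient-year at initiation, the 4-week figure is 1 − exp(−5 × 0.0767) = 31.8%, and maintenance at 0.10 overtakes it only after 5 × 0.0767 / 0.10 = 3.8 years.

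**Step 3: how much of the maintenance figure is time?** Let the cumulative hazard be −ln(0.9) × t^k, which fixes 10% at 1 year. With k = 1 the rate is constant. Smaller k means that reactions cluster early.

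| k | 1 year | 2 years | 5 years | 10 years |
|---|---|---|---|---|
| 0.3 | 10.0% | 12.2% | 15.7% | 19.0% |
| 0.5 | 10.0% | 13.8% | 21.0% | 28.3% |
| 1.0 | 10.0% | 19.0% | 41.0% | 65.1% |

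The percentage rises with time in every row, but by very different amounts. The planned table would not let a reader tell which row applies.

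**The case against.** The strongest reply is that this is a descriptive table on a matter outside the study objectives. The SAP tabulates the phases separately and plans no contrast or test between them. Protocol 9.9 already warns against comprehensive safety conclusions, and the listing of onset dates lets timing be inspected. All of this stands, and it limits the weight of the point. The warning in 9.9, however, rests on the absence of patients who discontinued. It does not mention unequal observation time.

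A second reply is that SAP 7.7 does not use the word percentage, and that its sentence may cover only events after authorization, not the block split by phase. Both readings are possible. Neither rescues the table. If 7.7 does not govern the phase block, the default in 7.1 gives percentages anyway. If a true rate is meant, its time base is missing.

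Three stronger readings are tempting, and the documents do not support them:

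- A reader might infer that initiation lasts weeks and maintenance many years. No phase length is stated. Protocol 9.2.7.7 lists the nasojejunal tube, the PEG-J procedure and titration as separate items, so initiation cannot simply be equated with titration.
- A reader might infer that the maintenance figure mostly reflects time on LCIG. That needs a roughly constant hazard (Step 3).
- A reader might infer that maintenance will look the riskier phase. That depends on the assumed rates (Step 2).

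**Conclusion.** The point holds as one of definition and interpretation in a safety summary. The adverse reaction figures are patient-based percentages without time at risk, for two phases that are not delimited. Maintenance observation differs between patients, so the maintenance percentage depends on time on LCIG by an unknown amount, and the two phase percentages are not comparable as risks.

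The size cannot be fixed from the documents. Under the assumptions shown, 10% at 1 year corresponds to anything from 19% to 65% at 10 years. The conclusion rests on reading the rates in 7.7 as percentages, which 6.6, 7.1 and 7.4 support strongly without saying so outright. The primary endpoint is untouched. The change is worth making because it is cheap and gives figures that can be interpreted.

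**What to change.** In SAP 6.6 and 7.7:

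1. Define the start and end of each phase, and assign events to phases by onset date on that same boundary. Titration duration can serve as time at risk for initiation only if the phase is defined to match it.
2. Label the crude figures as the percentage of patients with at least one event, and show the distribution of observation time beside them.
3. Add the percentage of patients with a reaction in the first 12 months after LCIG initiation. Every eligible patient has completed this window. The day count in SAP 6.4 can be reused: 12 × 30.4 = 364.8, rounded to 365 days.
4. Add events per 100 patient-years by phase, with time in that phase as the denominator. Any first-event rate must stop each patient's time at the first event. Note that LCIG treatment duration is a calendar span that includes interruptions, since eligibility requires only 80% of days in the preceding year.
5. State that all figures describe only patients still on LCIG, as follows from Protocol 9.9.

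The cost is SAP wording and one added table, with no new data. There are two drawbacks. Events with incomplete onset dates cannot be placed; the SAP has no rule for them, so their number should be reported. Retrospective chart recording may also be uneven over the years, so the patient-year rates should be presented as descriptive averages.
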